17. DATA SAFETY MONITORING BOARD (DSMB) AND SAFETY OFFICER

The DSMB will consist of at least external 3 members. Additionally one independent medical safety officer will monitor the study. On a monthly basis, the Data Management Center (DMC) will issue standard safety reports (enumerated by event and category, both by total and by type) as well as a cumulative report of all Adverse Events (AEs) to include Event Code, Dates of Onset/Resolution, Grade, and Outcome to the an independent safety officer. In addition, these standard safety reports will be presented to the DSMB at each conference. The DSMB will review these data and make appropriate safety decisions based on these events. Participants will be monitored for potential AEs, including signs or symptoms related or unrelated to the condition under study, any clinically significant laboratory abnormality, or any abnormality detected during physical examination.

18. RANDOMIZATION, DATA MANAGEMENT AND DATA MONITORING

The randomization of the study patients and the processing and analysis of the data will be carried out by the Biostatistics core of the Center for Gastrointestinal Biology and Disease at UNC Chapel Hill.

Study data for this study will be collected and stored using electronic records. Data captured will be entered in real time at each clinical site using web forms developed to replicate paper case report forms. All data will be created, modified, maintained, archived, retrieved and distributed by a computer system. The use of electronic records will increase the speed of data collection and exchange. This will reduce the manpower necessary to perform double-data entry from paper forms and transcription error. In addition, electronic records permit economical storage of study data and ease of accessibility and analysis. Data management and data quality systems will be built into the system.

Data quality using electronic records will ensure that data are attributable, legible, contemporaneous and original.

The DMC at the CGIBD at the University of North Carolina will track the data collection, provide data security, control for confidentiality of study data, maintain computer backups to protect data until study closure and archive study data according to FDA requirements (21 CFR 11). Electronic signatures will be linked to each entry.

All computer systems and programs will be password protected, and all electronic communications of study and other confidential information will be encrypted. Personnel at the CGIBD have extensive training and experience using electronic data systems. Good computer security practice (restricting physical access to machines, prohibition of password sharing, and logging off computers after work hours or when away from the machine) will be required of all study personnel.

Standard Operating Procedures exist for users of the DMC. Only authorized persons are authorized for data entry and access. Data security systems require password protected identification codes for data entry and provide protection against data manipulation. The database is located on a server protected by firewalls. Access to the database server will not be allowed by users on computers outside of the firewall-

protected zone. Virus protection software is installed on each study machine. System access to computer systems will be audited. Redundant backups and off-site backup storage will allow for quick restoration of data in the unlikely event that a hardware failure, disaster, or security breach should occur. Servers and backups will be located in a secured location with access limited to authorized personnel.

Data cleaning will include range and edit checks, cross form edit checks, query generating and tracking and periodic data status reports. Any data errors or inconsistencies detected after data entry will be automatically tracked, communicated and resolved using a web-based application. An audit trail of all data changes over the life of the study will be maintained. All study raw data, forms, documents, software programs, software applications and computer data files will be indexed and archived routinely. Strict version control of documents and software applications will be instituted. Retention of study documentation after study completion will conform to FDA and NIH requirements.

Standardized study management reports will be generated monthly during the recruitment phase of the study. These reports will be used to track study progress including study patient enrollment, randomization, compliance, study patient status changes, and study events. The data will be reported for each Study Center individually and summarized for the study as a whole. Every six months, a standardized report will also be generated for the DSMB meeting. This report will include additional information on clinical events and adverse events that is coded by blinded treatment group. Other than the study statistician and statistical analyst, no study personnel will see this report.

19. MODIFIED POUCHITIS DISEASE ACTIVITY INDEX (PDAI)

The Pouchitis Disease Activity Index (PDAI) was developed by Sandborn et al for diagnosing active pouchitis and quantifying the severity of pouchitis ⁶⁶. Shen et al. later on modified the index (mPDAI) and showed that similar outcomes can be measured after omitting the evaluation of histology, thus omitting the biopsy and histology costs.⁶⁷ The PDAI or the modified PDAI has been used in a number of clinical studies where it appears quite useful in discriminating between subjects with and without pouchitis and in quantifying the severity of pouchitis ^{20, 22, 25, 27-29, 68-70}

• Subject Data Collected via Diary Card

Subjects will be instructed to complete the diary at the same time each night before going to bed. The following information will be collected daily using a subject completed diary card:

- Current daily stool number via the question, "During the past 24 hours how many bowel movements did you have?" (Provide number)
- Rectal bleeding via the question, "During the past 24 hours, what percentage of your bowel movements contained blood?" a. 0% (none); b. <20% (rare); c.≥20% (usual)
- Fecal urgency/abdominal cramps via the question, "During the past 24 hours what percentage of your bowel movements were preceded with abdominal cramps or an urgent need to go to the bathroom?" a. 0% (none); b. <50% (occasional); c. ≥50% (usual)
- Fever defined as temperature >37.8°C via the question, "During the past 24 hours have you experienced a fever higher than 37.8°C (100.0°F) (Yes/No)

Please note that responses to the rectal bleeding and fecal urgency questions are each associated with a word in parentheses. These words are the ratings that are used on the mPDAI. For example, if on a given day a subject responds that their percentage of bowel movements that had blood present was <20% and the percentage of bowel movements that were preceded by abdominal cramps was 0%, then their

rectal bleeding and fecal urgency/abdominal cramps mPDAI ratings would be "rare" and "none", respectively.

The rectal bleeding frequency will be calculated for the three evaluation days. The relative frequency for rectal bleeding will be calculated based on the total number of stools passed over the same three evaluation days ((total #stools with blood/total #stools)*100). The relative frequency will be evaluated against the following categories:

0% (none) < 20% (rare) > 20% (present daily)

Please note that the words, "none", "rare", and "present daily" in parentheses, correspond to the rectal bleeding categories on the mPDAI. These categories will be used to assign a mPDAI score for rectal bleeding.

Fecal urgency/abdominal cramping

The fecal urgency/abdominal cramping frequency will be calculated for the three evaluation days. The relative frequency for fecal urgency/abdominal cramping will be calculated based on the total number of stools for the same three evaluation days ((total #stools with cramping or urgency/total #stools)*100). The relative frequency will be evaluated against the following categories:

0% (none) < 50% (occasional) > 50% (frequent)

As with rectal bleeding, the words, "none", "occasional", and "frequent" in parentheses, correspond to the fecal urgency/abdominal cramping categories on the mPDAI. These categories will be used to assign a mPDAI score for fecal urgency/abdominal cramping.

Fever

If a subject indicates that they had a fever on none of the three evaluation days, the mPDAI score for "absent" will be recorded. If a subject indicates that they had a fever on one or more of the three evaluation days, the mPDAI score for "present" will be recorded.

20. STATISTICAL ANALYSIS

The following endpoints will be assessed

• Primary Endpoint:

Safety and Tolerability of FMT

- Number of study patients, who discontinued therapy
- Adverse events grouped by body system
- Changes in laboratory values
- Secondary Endpoints Clinical remission (mPDAI score <4 points and a decrease in the baseline mPDAI > 2 points) and no need for antibiotic therapy at week 4.
- Clinical remission (clinical mPDAI score ≤ 4) and no need for antibiotics at week 8*.
- Clinical remission (clinical mPDAI score ≤ 4) and no need for antibiotics at week 16*.
- Endoscopic improvement of active pouchitis (decrease from baseline in mPDAI endoscopic subscore ≥ 2 points) at week 4.
- Response: Symptomatic improvement of active pouchitis (decrease from baseline in mPDAI clinical subscore ≥ 2 points) and no need for antibiotic therapy at week 4.
- Response: Symptomatic improvement of active pouchitis (decrease from baseline in mPDAI clinical subscore ≥ 2 points) and no need for antibiotic therapy at week 8*.
- Response: Symptomatic improvement of active pouchitis (decrease from baseline in mPDAI clinical subscore ≥ 2 points) and no need for antibiotic therapy at week 16*.

*Only patients who do not continue in open label extension

- Exploratory analyses (OL=Open label):
- Endoscopic improvement of active pouchitis (decrease from baseline in mPDAI endoscopic subscore ≥ 2 points) at in open label extension week 8.

- Clinical remission (mPDAI score ≤4 points and a decrease in the baseline mPDAI> 2 points) and no need for antibiotic therapy at week 10 OL.
- Clinical remission (clinical mPDAI score ≤ 4) and no need for antibiotics at week 14 OL.
- Clinical remission (clinical mPDAI score ≤ 4) and no need for antibiotics at week 22 OL.
- Response: Symptomatic improvement of active pouchitis (decrease from baseline in mPDAI clinical subscore ≥ 2 points) and no need for antibiotic therapy at week 10 OL.
- Response: Symptomatic improvement of active pouchitis (decrease from baseline in mPDAI clinical subscore ≥ 2 points) and no need for antibiotic therapy at week 14 OL.
- Response: Symptomatic improvement of active pouchitis (decrease from baseline in mPDAI clinical subscore ≥ 2 points) and no need for antibiotic therapy at week 22 OL.
- Symptomatic worsening of active pouchitis (decrease from baseline in mPDAI clinical subscore ≥ 2 points) from FMT week 0 week 16
- Quantitative changes in mPDAI from baseline values
- Quantitative changes of calprotectin from baseline
- Alterations in stool microbiome after FMT
- Engraftment of donor FMT

Clinical analyses

The primary endpoint is the evaluation of safety and tolerability of FMT in patients with ADP. Secondary endpoints are endoscopic and clinical remission at week 4 in conjunction with no need for antibiotic therapy, clinical response and remission and no need for antibiotics at week 4,8 and 16, endoscopic improvement of pouchitis and quantitative changes of calprotectin after the initial FMT. All subjects with missing data for determination of endpoint status will be considered as a non-responder in the intention-to-treat analysis. For dichotomous outcomes we will compute the percentage of subjects having the event along with a 95% confidence interval. For continuous outcomes we will compute the mean and a 95% confidence interval for the mean as well as descriptive statistics such as median, range and upper and lower quartiles. In addition to computing these measures for all 20 subjects, we will compute them for subgroups of interest (e.g. endoscopic active vs inactive ADP). These estimates can then be used in the planning of a larger, hypothesis-based study.

• Sample size calculation

This trial is designed as a proof-of-concept study of FMT therapy, not a definitive evaluation of FMT therapy in patients with ADP. The goal is to evaluate the safety and feasibility of such a trial, as well as to estimate the effect sizes in placebo and FMT therapy groups in order to accurately estimate the sample size needed for subsequent evaluation in a larger definitive trial. Nonetheless, we estimated the minimum effect size this pilot study can detect. We assume a placebo remission rate (defined as clinical remission and no need for antibiotics) of 10%. The low placebo response rate is based on the inclusion criterion, which selects only patients needing continuous or recurrent antibiotic therapy in the setting of ADP. With a follow-up of 16 weeks with the requirement of clinical remission without antibiotic therapy at end of follow-up, a placebo response rate beyond 10% is highly unlikely. The recent case series of Stallmach et al. suggests an antibiotic-free remission rate of 80% and a response rate of 100% in the setting of repeated FMT.⁴⁹ With 20 patients (1:1 randomization), and a placebo response rate of 10%, we will have 80% power to detect an effect difference of 67.5%, that is, an antibiotic-free remission rate

of 77.5% in the treatment group (2-sided, alpha=0.05, Fisher-Irwin's exact conditional test). Thus, even with this small proof-of-concept design, we could observe a significant effect in the range of effect size reported in recent case series.

Microbiome Analyses

From each patient 1 stool sample will be collected before transplant and twice after the transplant (week 3 and 4). Patients in remission will collect 2 more stool samples in week 8 and 16. Patients in the open label extension trial will collect stool samples after transplant in week 8, 10, 14 and 22. Assuming that 9 patients enter remission in the placebo controlled phase (9x4= 36 samples) and 11 patients enter the open label extension (11x7=77 samples) a total of 116 samples will be analysed. All microbiome analyses will be conducted by OpenBiome, which will donate time and materials for the analyses. The gut microbiome of donors and patients will be analysed through deep sequencing of the 16S ribosomal RNA gene amplified from stool samples. Microbial engraftment will be operationalized through the donor similarity index (DSI) used to evaluate the degree of engraftment in FMT recipients over time (after 2,4,8 and16 weeks).⁶¹ We will measure DSI over time to elucidate the stability of engraftment and its relationship to clinical observations. In addition to 16S rRNA sequencing, we will save aliquots of stool for metabolomic characterization. In particular, given the potential role of butyrate in ameliorating inflammation, we're especially interested in measuring short chain fatty acid levels in stool before and after FMT. We plan to collect stool samples for characterization at baseline and at 2, 4, 8 and 16 week intervals after treatment.

21. STUDY VISITS CHART

1.1 STUDY VISITS CHART PLACEBO CONTROLLED TRIAL SCREENING – WEEK 4 (SITE VISIT)

Visit	Screening	1	2	3	4	5	Early termination ^g
Type of visit	Site	Site	Phone	Site	Phone	Site	Phone/site
Derr	-14	0	7	15	26	28	
Day	-14	0	+/-1	+3	+/-1	+/-3	
Week	-2	0	1	2	4	4	
Medical History	Х						
mPDAI score		Х	Xd	X ^d	X ^{g(!)}	Х	X
Concomitant Medication	Х	Х	X	X	X	Х	X
Adverse Events		Х	X	Х	Х	Х	X
Physical Exam	Х					Х	Х
Blood Tests	Х					Х	Х
Pregnancy Test (urine)	Х	Х					
Test FMT capsule	Х						
Dispense FMT capsules		Х					
10-14 day antibiotic therapy pre- transplant	Х				Xc	Xc	Xc
Stool sample	Xe			X ^f	X ^f	X ^g	Х
Sigmoidoscopy (Pouchoscopy		Х				Xa	
Endoscopic FMT		Х					
Distribute/Review Subject Diaries ^b	Х	Х	Х	Х	Х	Х	Х
Distribute/Review Subject adverse events diary ^b			Х	X	X	X	Х

Study visits Chart for patients continuing in observation phase

Visit	6	7	8	9	Early termination ^g
Type of visit	Phone	Site	Site	Phone	Phone/site
Day	42	56	112	168	
	+/-3	+/-5	+/-7	+/-10	
Week	6	8	16	24	
mPDAI score	Х	X ^d	X ^d		Х
Concomitant Medication	Х	Х	X		Х
Adverse Events	Х	Х	X	X ^I	Х
Physical Exam		Х			Х
Blood Tests ^a		Х			Х
Stool sample		Xf	Xf		
Sigmoidoscopy (Pouchoscopy					
Distribute/Review Subject Diaries ^b	Х	Х			Х
Distribute/Review Subject adverse events diary ^b	Х	Xj			X

1.2 STUDY VISITS CHART OPEN LABEL EXTENSION FOR PATIENTS WITH RESPONSE ONLY OR NO RESPONSE OR EARLY TERMINATION DUE TO FLARE IN PLACEBO-CONTROLLED TRIAL SECTION

Visit	60L	70L	80L	90L	100L	110L	120L	130L	Early termination ^g
Type of visit	Site	Phone	Site	Site	Phone	Site	Site	Phone	Phone/site
Day (post 2nd transplant)	38 (0)	46 (8)	53 (15)	66 (28)	80 (42)	94 (56)	150 (112)	206 (168)	
38 (0)	38 (0)	+/-1	+3	+/-3	+/-3	+/-5	+/-7	+/-10	
Week (post 2nd transplant)	6 (0)	7 (1)	8 (2)	10 (4)	12 (6)	14 (8)	22 (16)	30 (24)	
mPDAI score		X ^d	X ^d	Х	Х	X ^d	X ^d		Х
Concomitant Medication	Х	Х	Х	Х	Х	Х	Х		Х
Adverse Events	Х	Х	Х	Х	Х	Х	Х	XI	Х
Physical Exam	Х			Х		Х			Х
Blood Tests				Х		Х			Х
Pregnacy test (urine)	Х								
Dispense FMT capsules + omeprazole	X ^g								
Stool sample			Xf	Xf		Xf	Xf		Х
Sigmoidoscopy (Pouchoscopy	Х			Х					
Endoscopic FMT	X ^h								
Distribute/Review Subject PDAI Diary ^b	Х	Х	Х	Х	Х	Х	Х		X
Distribute/Review Subject adverse events diary ^b	Х	Х	Х	Х	Х	Xj			X

^a Pouchoscopy visit 5 only in patients who are in remission (mPDAI<4) as assessed in visit 4 by phone or in patients with clinical active pouchitis, but not willing to participate in open label extension

^b There will be two subject diaries provided to the patient: One for the evaluation of the mPDAI will be provided at Screening. The study patient will complete this diary each day, beginning with the Screening visit, and ending with the Week 16 visit. Stool frequency, rectal bleeding, fecal urgency or abdominal cramps, and/or fever will be recorded. A minimum of three days of diary entries will be required during the week prior to randomization, Phone visit week 1 and 2 and Visit Week 4 and 8. The last three days of diary entries will be used to calculate stool frequency and fecal urgency/abdominal pain scores and clinical mPDAI subscores.

The "adverse events diary" will assess for adverse events during the FMT phase (14 days) and daily for 28 days after the last day of oral FMT.

^c Visit 4: Start of pretransplant antibiotic therapy for 10-14 days only in patients qualifying for open label extension

^d Clinical mPDAI.

^e Stool samples for microbiome, calprotectin and C. diff analyses.

^fStool samples for calprotectin and microbiome analyses.

[figure not shown]
^g between visit 1-5 or visit 6-8 or visit week 6OL-12OL

^h Endoscopic open label FMT followed by oral FMT only if no clinical remission according to mPDAI at visit 4 and study patients wants to continue in open label FMT.

¹ Evaluation of serious adverse events occurring in the follow-up period

^jCollect adverse event diary

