	The outcome will be determined by the modified pouchitis disease activity index (mPDAI) and the need for antibiotic therapy to control symptoms. The mPDAI is a composite index consisting of 2 disease variables (clinical criteria of pouchitis: number of bowel movements, blood in stool, urgency and fever with a maximum score of 6 and endoscopy criteria of pouch inflammation with a maximum score of 6. The maximum combined score is 12).	
	 Complete remission is defined as a mPDAI score = 0 and no need for antibiotics. Clinical remission is defined as a clinical mPDAI score ≤ 4 and no need for antibiotics. Symptomatic improvement is defined as a decrease from baseline in the mPDAI clinical subscore of 2 points and no need for antibiotics. Symptomatic worsening of the disease is defined by an increase in the mPDAI clinical subscore of 2 points or the need for antibiotics. 	
	The severity of the pouch inflammation will be evaluated by two pouchoscopies (week 0 and week 4). Endoscopic improvement is defined as a decrease from baseline in the mPDAI endoscopic subscore of 2 points.	
Primary variables	Safety and tolerability of endoscopically and orally applied FMT	
Secondary variables:	 Clinical remission (mPDAI score ≤4 points) and no need for antibiotic therapy at week 4. Clinical remission (clinical mPDAI score ≤ 4) and no need for antibiotics at week 8*. Clinical remission (clinical mPDAI score ≤ 4) and no need for antibiotics at week 16*. Endoscopic improvement of active pouchitis (decrease from baseline in mPDAI endoscopic subscore ≥ 2 points) at week 4. 	

	 Response: Symptomatic improvement of active pouchitis (decrease from baseline in mPDAI clinical subscore ≥ 2 points) and no need for antibiotic therapy at week 4. Response: Symptomatic improvement of active pouchitis (decrease from baseline in mPDAI clinical subscore ≥ 2 points) and no need for antibiotic therapy at week 8*. Response: Symptomatic improvement of active pouchitis (decrease from baseline in mPDAI clinical subscore ≥ 2 points) and no need for antibiotic therapy at week 8*. Response: Symptomatic improvement of active pouchitis (decrease from baseline in mPDAI clinical subscore ≥ 2 points) and no need for antibiotic therapy at week 16*. 	
	*Only patients who do not continue in open label extension	
	• Exploratory analyses (OL=Open label):	
	 Endoscopic improvement of active pouchitis (decrease from baseline in mPDAI endoscopic subscore ≥ 2 points) at in open label extension week 8. 	

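### Symptomatic worsening is written as an improvement in score, and late clinical remission contains every responder, so it should be labelled and reported as a symptom-only outcome

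*Combined protocol and SAP*

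**What the plan says.** **Worsening.** The exploratory analyses in section 20 list "Symptomatic worsening of active pouchitis (decrease from baseline in mPDAI clinical subscore ≥ 2 points", counted from week 0 to week 16. The endpoint lists in sections 1 and 5 use the same direction. The evaluation criteria in section 1 say instead: "Symptomatic worsening of the disease is defined by an increase in the mPDAI clinical subscore of 2 points or the need for antibiotics".

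**Remission at visits without endoscopy.** Section 20 lists "Clinical remission (clinical mPDAI score ≤ 4) and no need for antibiotics at week 16". Week 8 is worded the same way, as are week 14 OL and week 22 OL ("Clinical remission (clinical mPDAI score ≤ 4) and no need for antibiotics at week 22 OL"). Weeks 8 and 16 carry the footnote "Only patients who do not continue in open label extension".

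**Response at the same visits.** This is "decrease from baseline in mPDAI clinical subscore ≥ 2 points) and no need for antibiotic therapy at week 16", with matching wording at the other three visits.

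**Scale.** Section 1 gives the clinical part of the mPDAI a maximum of 6 and the total a maximum of 12. Appendix C gives the items. Section 19 sets active disease at 5 or more on the total score. The visit charts in section 21 show no pouchoscopy at these four visits and mark them as clinical mPDAI only.

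**Baseline.** Section 19 scores baseline from the three days before week 0. Section 7 has all patients on antibiotics for at least 10 days before the endoscopic transplant, stopping 24 hours before it.

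**The concern.** The worsening endpoint and the response endpoint describe the same movement of the same score. An analyst who programs section 20 literally would report improvers as worsened and would miss patients whose symptoms rose.

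The remission cut raises a question of interpretation. Four is the highest non-active value on the 0-12 total, but at these visits it is applied to a 0-6 subscore, and no section explains that choice. Section 19 supports the index in general, not this cut. Section 20 says the trial should supply effect sizes for planning a larger one. A planner who took the week-16 remission rate as stricter than the response rate, or as equivalent to the week-4 total-score rate, would carry the wrong quantity forward.

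**Working it through.** **Inputs.** Appendix C: stool frequency 0-2, rectal bleeding 0-1, urgency/cramps 0-2, fever 0-1. The maximum is 2 + 1 + 2 + 1 = 6, which reproduces the figure in section 1. The definitions are those set out above.

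**Step 1: worsening against response.** Let b be the baseline and f the follow-up subscore, each 0 to 6, giving 7 × 7 = 49 pairs.
- Fall of 2 or more (b − f ≥ 2): 1 + 2 + 3 + 4 + 5 = 15 pairs. All 15 meet the response score condition, and all 15 meet worsening as listed in section 20.
- Rise of 2 or more: 15 pairs. None meets worsening as listed.
- Rise of exactly 2, the literal size in the section 1 definition: 5 pairs. Reading it as exactly 2 leaves out 15 − 5 = 10 pairs with larger rises, so the size needs settling as well as the direction.
- The section 1 definition also counts a need for antibiotics; the listed endpoint does not.

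**Step 2: response implies remission.** Since b ≤ 6, a fall of 2 or more gives f ≤ 6 − 2 = 4. Both endpoints carry the same antibiotic-free condition. The result therefore holds whichever baseline is used for the open-label visits, and scoring missing data as non-response does not alter it.

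| Cut on clinical subscore | Response pairs meeting it (of 15) | Response pairs failing it (b to f) |
|---|---|---|
| 4 or less | 15 | none |
| 3 or less | 14 | 6 to 4 |
| 2 or less | 12 | 5 to 3, 6 to 3, 6 to 4 |

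**Step 3: what the cut excludes.** There are 3 × 2 × 3 × 2 = 36 item patterns. The numbers scoring 0 to 6 are 1, 4, 8, 10, 8, 4 and 1.
- 4 or less: 1 + 4 + 8 + 10 + 8 = 31 pass.
- 3 or less: 23 pass. 2 or less: 13 pass.
- Without fever or daily bleeding there are 3 × 3 = 9 patterns. All 9 pass at 4 or less, including top stool frequency with top urgency/cramps (2 + 0 + 2 + 0 = 4). At 2 or less, 6 pass.

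**Step 4: overlap with worsening once its direction is corrected.** With a rise of 2 or more, 6 of 15 pairs still end at 4 or less (0 to 2, 0 to 3, 0 to 4, 1 to 3, 1 to 4, 2 to 4). With a rise of exactly 2, it is 3 of 5. At a cut of 2 or less, one pair (0 to 2) remains on either reading.

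**Step 5: one patient.** With 20 patients allocated 1:1, one patient off antibiotics with a subscore of 3 or 4 moves an arm's rate by 1/10 = 10 points under a cut of 2. The step is larger if extension patients leave the denominator.

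**The case against.** The strongest reply concerns baseline. Patients are scored after an effective course of antibiotics, so low baseline subscores are to be expected, although the documents give no distribution. A patient at 0 or 1 cannot fall by 2 and so can never be a responder, yet staying at 0 off antibiotics is the success sought in antibiotic-dependent disease. This stands. A reader might infer that counting patients without improvement as remitters is a fault, or that a remission rate above the response rate signals an error. Neither follows: the non-response pairs that pass include 0 to 0, 1 to 0 and 1 to 1.

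The second reply is that a stricter cut changes little. This also stands. From any baseline of 4 or less, a fall of 2 or more ends at 2 or less, so only baselines of 5 or 6 can yield a responder outside a cut of 2. No document validates 2 either, so replacing the stated cut is a trade-off rather than a correction.

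Other stronger readings lack support:
- The sentence "suggests an antibiotic-free remission rate of 80% and a response rate of 100% in the setting of repeated FMT" and the chart title "STUDY VISITS CHART OPEN LABEL EXTENSION FOR PATIENTS WITH RESPONSE ONLY OR NO" might suggest that remission is meant to be stricter than response at these visits. The first reports a cited case series whose definitions are not given. The second concerns entry to the extension around week 4.
- Section 20 prints a strict inequality for week-4 remission where sections 1 and 5 print 4 or less. The contents entry for that same heading also prints 4 or less, so a text-extraction slip is likely.
- A lenient cut might seem to undermine the 10% placebo assumption. Section 20 rests that figure mainly on antibiotic dependence, and the stated 80% power reproduces at 80.2% (two-sided Fisher exact test, 10 per arm, 10% against 77.5%).

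None of these replies touches the reversed direction of worsening.

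**Conclusion.** The worsening endpoint is wrong as written. In three sections it has the opposite direction to the definition in section 1 and the same score change as response.

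The remission finding is narrower. At weeks 8, 16, 14 OL and 22 OL remission contains every responder by arithmetic, so it cannot be read as the stricter outcome. Since 31 of 36 patterns pass the score cut, most of the discrimination comes from the antibiotic-free condition. The wording is consistent and may be deliberate, so this calls for labelling and a sensitivity analysis, not a new definition. The containment does not carry over to week 4 or week 10 OL if remission there uses the total score: a patient falling from 2 to 0 on the clinical part with an endoscopic score of 5 responds but totals 5.

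This rests on Appendix C scoring and on the charts' marking of these visits as clinical mPDAI only. The counts are unweighted patterns, not patient frequencies. The endpoints concerned are secondary or exploratory in a proof-of-concept trial whose primary endpoint is safety. Response, quantitative mPDAI and calprotectin changes are also reported, which limits the harm.

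**What to change.** 1. In the endpoint lists of sections 1, 5 and 20, change the direction of symptomatic worsening from decrease to increase. Align the size of the change (2, or 2 or more) and the antibiotic component with the definition in section 1. This costs only wording.
2. Keep the stated remission definition at weeks 8, 16, 14 OL and 22 OL, but label it symptomatic remission (clinical subscore) without antibiotics in sections 1, 5 and 20.
3. Report by arm the distribution of the clinical subscore among antibiotic-free patients, plus one stricter cut pre-specified before unblinding as a sensitivity analysis, with 95% confidence intervals. The diary already supplies the data. The cost is one extra table row per visit and possibly less favourable rates.
4. State that at 4 or less remission includes all responders, and that these rates are not interchangeable with week-4 total-score remission when planning the larger trial.

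Two separate matters need reconciling by the sponsor. Section 7 puts a score of exactly 4 on both sides of the visit-4 decision, while section 8 does not; no rule is proposed here. Also, an exploratory endpoint names endoscopic improvement at week 8 of the extension, where the charts schedule no pouchoscopy.
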